8.5 Pregnancy

Pregnancy, in and of itself, is not regarded as an AE unless there is suspicion that study drug or process may have interfered with the effectiveness of a contraceptive medication or method. When a pregnancy has been confirmed in a subject during maternal or paternal exposure to study drug and/or process, the following procedures should be followed to ensure subject safety:

Data on fetal outcome are collected for regulatory reporting and drug safety evaluation. Follow-up should be conducted for each pregnancy to determine outcome, including spontaneous or voluntary termination, details of the birth, and the presence or absence of any birth defects, congenital abnormalities, or maternal and/or newborn complications.

8.6 Protocol Exceptions and Deviations

Exception (Prospective action)

An *exception* is defined as a one-time, intentional action or process that departs from the approved study protocol, intended for one occurrence. If the action disrupts the study progress, such that the study design or outcomes may be compromised, or the action compromises the safety and/or welfare of study subjects, advance documented approval from the Regulatory Sponsor and local regulatory review committees, per institutional guidelines, is required. Approval from the Regulatory Sponsor must be received prior to submission to the local regulatory review committees.

Deviation (Retrospective action)

A *deviation* is defined as a one-time, unintentional action or process that departs from the approved study protocol, involving one incident and identified retrospectively. If the deviation disrupts study progress, such that the study design or outcomes may be compromised, or the deviation compromises the safety and/or welfare of study subjects, the deviation must be reported to the Regulatory Sponsor within 5 days of PI knowledge and to local regulatory review committees per institutional guidelines.

Report the following information on the Sponsor's exception/deviation form:

- Protocol number
- Subject number
- Description of the exception or deviation
- Rationale
- Impact on subject safety
- Impact on data integrity

Page 59 of 72

Deviations that are assessed by the PI to not disrupt the study progress, such as not affecting the study design or outcome, or compromising the safety and/or welfare of study subjects, should be documented in site records and contain documentation of the PI's assessment.

8.7 Stopping Rules (safety and efficacy)

The safety analysis is based on Bayesian probability calculations and will be performed after the first 6 subjects treated at the RP2D and then after enrollment of 9, 12, and 15 subjects at RP2D dose. The maximum rate of unacceptable toxicity (AEs that would fit the definition of DLT from phase 1 at any point or AEs that do not allow the subject to restart treatment within 28 days) is 30% and a beta prior of (1,5) is assumed (that is 1 unacceptable toxicity in 6 subjects). The study will be terminated if 4 unacceptable toxicities in 6 subjects, 5 in 9, 6 in 12, or 7 in 15 are observed. The posterior probability that the true rate of unacceptable toxicities is above 30% at each stopping would be around 77 to 79% (79%, 78%, 78%, and 77%, respectively).

The efficacy analysis is based on Simon 2 stage optimal design and will be performed after the enrollment of the first 9 evaluable subjects treated at the RP2D. If there are no responders with CR from the first 9 evaluable subjects (at the 8 week or 16 week response assessment, at any itacitinib dose level), the null hypothesis (CR rate of 5% or lower with the new combination) will be considered as supported, and the study will be terminated. The study will be considered successful if the total number of subjects with CR is ≥ 2 in Phase II (at the 8 week or 16 week response assessment).

If there are two (2) study related deaths during the phase I portion of the trial, the study will be terminated.

Any death in the Phase II portion will result in pausing enrollment of the study until investigation is completed. If there are two (2) study related deaths in the Phase II portion of the study will be terminated.

8.8 Monitoring

This study will be monitored according to the Sponsor Data and Safety Monitoring Plan.

The investigator will allocate adequate time for such monitoring activities. The Investigator will also ensure that the monitor or other compliance or quality assurance reviewer is given access to all the above noted study-related documents and study related facilities (e.g. pharmacy, diagnostic laboratory, etc.), has adequate space to conduct the monitoring visit, and that site staff, including the PI, can meet with the monitor to discuss findings.

8.9 Auditing and Inspecting

The investigator will permit study-related monitoring, audits, and inspections by the IRB, the sponsor, government regulatory bodies, and University compliance and quality assurance groups of all study related documents (e.g. source documents, regulatory documents, data collection instruments, study data etc.). The investigator will ensure the capability for inspections of applicable study-related facilities (e.g. pharmacy, diagnostic laboratory, etc.).

Version 11.0 Page 60 of 72

Participation as an investigator in this study implies acceptance of potential inspection by government regulatory authorities and applicable University compliance and quality assurance offices.

Notify the Sponsor in real-time if an audit/inspection notification is received.

9 STUDY ADMINISTRATION, DATA HANDLING AND RECORD KEEPING

9.1 Confidentiality

Information about study subjects will be kept confidential and managed according to the requirements of the Health Insurance Portability and Accountability Act of 1996 (HIPAA). Those regulations require a signed subject authorization informing the subject of the following:

- What protected health information (PHI) will be collected from subjects in this study
- Who will have access to that information and why
- Who will use or disclose that information
- The rights of a research subject to revoke their authorization for use of their PHI.

In the event that a subject revokes authorization to collect or use PHI, the investigator, by regulation, retains the ability to use all information collected prior to the revocation of subject authorization. For subjects that have revoked authorization to collect or use PHI, attempts should be made to obtain permission to collect at least vital status (i.e. that the subject is alive) at the end of their scheduled study period.

9.2 Source Documents

Source data is all information, original records of clinical findings, observations, or other activities in a clinical trial necessary for the reconstruction and evaluation of the trial. Source data are contained in source documents. Examples of these original documents, and data records include: hospital records, clinical and office charts, laboratory notes, memoranda, subjects' diaries or evaluation checklists, pharmacy dispensing records, recorded data from automated instruments, copies or transcriptions certified after verification as being accurate and complete, microfiches, photographic negatives, microfilm or magnetic media, x-rays, subject files, and records kept at the pharmacy, at the laboratories, and at medico-technical departments involved in the clinical trial.

9.3 Case Report Forms

The study case report form (CRF) is the primary data collection instrument for the study. All data requested on the CRF must be recorded. All entries will be entered into an electronic data capture system (EDC) via PennCTMS/VELOS. The Principal Investigator is responsible for assuring that the data entered into eCRF is complete, accurate, and that entry and updates are performed in a timely manner.

Version 11.0 Page 61 of 72

9.4 Data Collection and Management

For subjects having entered the survival follow-up period of the study, the site will use continuing subject records to supply data on subsequent treatment regimens, tumor assessments (if discontinued treatment for a reason other than progression), and OS in the eCRF. For subjects who do not intend to return to the study investigator for their ongoing care, follow-up should be maintained by phone contact, subject records, and public records/databases at intervals of about 12 weeks.

If the subject discontinues study treatment and actively withdraws consent for collection of follow-up data (e.g., subsequent anticancer treatments and survival), then no additional data collection should occur; however, subjects will have the option of withdrawing consent for study treatment but continuing in the follow-up period of the study for safety/efficacy assessments.

9.5 Records Retention

The Investigator must ensure that the records and documents pertaining to the conduct of the study and the distribution of the protocol therapy, that is copies of CRFs and source documents (original documents, data, and records [e.g., hospital records; clinical and office charts; laboratory notes; memoranda; subject's diaries or evaluation checklists; SAE reports, pharmacy dispensing records; recorded data from automated instruments; copies or transcriptions certified after verification as being accurate copies; microfiches; photographic negatives, microfilm, or magnetic media; x-rays; subject files; and records kept at the pharmacy, at the laboratories, and at medico-technical departments involved in the clinical study; documents regarding subject treatment and drug accountability; original signed informed consents, etc.]) be retained by the Investigator for as long as needed to comply with applicable regulations (at least 2 years after discontinuing clinical development or after the last marketing approval). The Investigator agrees to adhere to the document/records retention procedures by signing the protocol.

10 ETHICAL CONSIDERATIONS

This study is to be conducted in accordance with applicable US government regulations and international standards of Good Clinical Practice (FDA Title 21 part 312 and International Conference on Harmonization guidelines), and applicable institutional research policies and procedures.

This protocol and any amendments will be submitted to a properly constituted independent Institutional Review Board (IRB), in agreement with local legal prescriptions, for formal approval of the study conduct. The decision of the IRB concerning the conduct of the study will be made in writing to the investigator and a copy of this decision will be provided to the sponsor before commencement of this study.

All subjects for this study will be provided a consent form describing this study and providing sufficient information for subjects to make an informed decision about their participation in this study. This consent form will be submitted with the protocol for review and approval by the IRB for the study. The formal consent of a subject, using the IRB-approved consent form, must be obtained before that subject is submitted to any study procedure. This consent form must be signed by the subject and the investigator-designated research professional obtaining the consent.

Itacitinib + everolimus in HL

Version 11.0

Page 62 of 72

The protocol is listed on clinicaltrials.gov.

10.1 Risks

Refer the itacitinib investigator's brochure for the risks associated with itacitinib. Refer to section 5.6.2 and the everolimus package insert for the risks associated with everolimus.

10.2 Benefits

The combination of oral therapies has potential to be active in subjects with relapsed/refractory HL. Also, both agents are oral which makes this therapy convenient for subjects.

10.3 Risk Benefit Assessment

The potential benefits (effective oral therapy for subjects with limited options) outweigh the risks of this combination.

10.4 Informed Consent Process / HIPAA Authorization

The Investigator must obtain informed consent of a subject or his/her designee prior to any study related procedures. Documentation that informed consent occurred prior to the subject's entry into the study and the informed consent process should be recorded in the subject's source documents. The original consent form signed and dated by the subject and by the person consenting the subject prior to the subject's entry into the study, must be maintained in the Investigator's study files. A copy of the signed ICF must be provided to the study subject.

10.5 Conflict of Interest

All University of Pennsylvania Investigators will follow the University of Pennsylvania Policy on Conflicts of Interest Related to Research.

11 PUBLICATION PLAN

Publication of the results of this trial will be governed by University of Pennsylvania policies. Neither the complete nor any part of the results of the study carried out under this protocol, nor any of the information provided by the sponsor for the purposes of performing the study, will be published or passed on to any third party without the consent of the study sponsor. Any investigator involved with this study is obligated to provide the sponsor with complete test results and all data derived from the study.

Version 11.0 Page 63 of 72

13 APPENDIX

FACT-Lym Questionnaire 13.1

Below is a list of statements that other people with your illness have said are important. Please circle or mark one number per line to indicate your response as it applies to the past 7 days.

	PHYSICAL WELL-BEING	Not at all	A little bit	Some- what	Quite a bit	Very much
GP1	I have a lack of energy	0	1	2	3	4
GP2	I have nausea	0	1	2	3	4
GP3	Because of my physical condition, I have trouble meeting the needs of my family	0	1	2	3	4
GP4	I have pain	0	1	2	3	4
GP5	I am bothered by side effects of treatment	0	1	2	3	4
GP6	I feel ill	0	1	2	3	4
GP7	I am forced to spend time in bed	0	1	2	3	4
	SOCIAL/FAMILY WELL-BEING	Not at all	A little bit	Some- what	Quite a bit	Very much
GS1	I feel close to my friends	0	1	2	3	4
GS2	I get emotional support from my family	0	1	2	3	4
GS3	I get support from my friends	0	1	2	3	4
GS4	My family has accepted my illness	0	1	2	3	4
GS5	I am satisfied with family communication about my illness	0	1	2	3	4
GS6	I feel close to my partner (or the person who is my main support).	0	1	2	3	4
Q1	Regardless of your current level of sexual activity, please answer the following question. If you prefer not to answer it, please mark this box and go to the next section.					
GS7	I am satisfied with my sex life	0	1	2	3	4

Itacitinib + everolimus in HL
Version 11.0
Page 66 of 72

Please circle or mark one number per line to indicate your response as it applies to the past 7 days.

	EMOTIONAL WELL-BEING	Not at all	A little bit	Some- what	Quite a bit	Very much
GE1	I feel sad	0	1	2	3	4
GE2	I am satisfied with how I am coping with my illness	0	1	2	3	4
GE3	I am losing hope in the fight against my illness	0	1	2	3	4
GE4	I feel nervous	0	1	2	3	4
GE5	I worry about dying	0	1	2	3	4
GE6	I worry that my condition will get worse	0	1	2	3	4
	FUNCTIONAL WELL-BEING	Not at all	A little bit	Some- what	Quite a bit	Very much
GF1	FUNCTIONAL WELL-BEING I am able to work (include work at home)				_	
GF1		all	bit	what	bit	much
	I am able to work (include work at home)	all 0	bit 1	what	bit 3	much 4
GF2	I am able to work (include work at home)	all 0	bit 1 1	what 2 2	bit 3 3	much 4
GF2 GF3	I am able to work (include work at home)	0 0 0	bit 1 1	2 2 2	bit 3 3	4 4 4
GF2 GF3 GF4	I am able to work (include work at home)	0 0 0 0	bit 1 1 1 1	what 2 2 2 2	bit 3 3 3 3	4 4 4 4

Version 11.0 Page 67 of 72

Please circle or mark one number per line to indicate your response as it applies to the past 7 days.

	ADDITIONAL CONCERNS	Not at all	A little bit	Some- what	Quite a bit	Very much
P2	I have certain parts of my body where I experience pain	0	1	2	3	4
LEU1	I am bothered by lumps or swelling in certain parts of my body (e.g., neck, armpits, or groin)	0	1	2	3	4
BRM3	I am bothered by fevers (episodes of high body temperature)	0	1	2	3	4
ES3	I have night	0	1	2	3	4
LYM1	I am bothered by itching	0	1	2	3	4
LYM2	I have trouble sleeping at night.	0	1	2	3	4
вмт6	I get tired easily	0	1	2	3	4
C2	I am losing weight	0	1	2	3	4
Ga1	I have a loss of appetite	0	1	2	3	4
HI8	I have trouble concentrating.	0	1	2	3	4
N3	I worry about getting infections	0	1	2	3	4
LEU6	I worry that I might get new symptoms of my illness	0	1	2	3	4
LEU7	I feel isolated from others because of my illness or treatment	0	1	2	3	4
BRM9	I have emotional ups and downs	0	1	2	3	4
LEU4	Because of my illness, I have difficulty planning for the future.	0	1	2	3	4

Version 11.0 Page 68 of 72

13.2 Concomitant Medications/Products not to be taken

Examples of clinically relevant drug interaction: substrates, inducers and inhibitors of isoenzyme CYP3A4 and or P-gp (Note this is not an exhaustive list):

Excluded

Grapefruit, grapefruit products, Seville oranges (including marmalade containing Seville oranges), or starfruit

Strong CYP3A inhibitors:

boceprevir, clarithromycin, conivaptan, indinavir, itraconazole, ketoconazole, mibefradil, lopinavir/ritonavir, nefazodone, nelfinavir, ritonavir, posaconazole, saquinavir, telaprevir, telithromycin, voriconazole

Moderate CYP3A inhibitors:

amprenavir, aprepitant, atazanavir, ciprofloxacin, crizotinib, darunavir/ritonavir, diltiazem, erythromycin, fluconazole, fosamprenavir, imatinib, verapamil

Strong CYP3A inducers:

avasimibe, carbamazepine, phenobarbital, phenytoin, rifampin, St. John's wort

Moderate CYP3A inducers:

bosentan, efavirenz, etravirine, modafinil, nafcillin

Cautionary

Weak CYP3A inhibitors:

alprazolam, amiodarone, amlodipine, atorvastatin, bicalutamide, cilostazol, cimetidine, cyclosporine, fluoxetine, fluoxamine, ginkgo, goldenseal, isoniazid, nilotinib, oral contraceptives, pazopanib, ranitidine, ranolazine, tipranavir/ritonavir, ticagrelor, zileuton

Weak CYP3A inducers:

amprenavir, aprepitant, armodafinil, clobazamechinacea, pioglitazone, prednisone, rufinamide, vemurafenib

P-gp Inhibitor:

amiodarone, azithromycin, captopril, carvedilol, dronedarone, felodipine, quercetin, ronalzine, ticagrelor

Please note:

- strong inhibitor implies that it can cause ≥5-fold increase in AUC or ≥80% decrease in clearance of sensitive CYP substrates
- moderate inhibitor implies that it can cause 2 to 5-fold increase in AUC values or 50-80% decrease in clearance of sensitive CYP substrates (the distinction is not always categorical as interaction can vary according to conditions).

Itacitinib + everolimus in HL
Version 11.0
Page 69 of 72

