4.2 Exclusion Criteria

- 1. Unable to sign informed consent form.
- 2. Pregnant or breast-feeding females (lactating females must agree not to breast feed while taking the investigational agents).
- 3. Any condition, including the presence of laboratory abnormalities, which places the subject at unacceptable risk if he/she were to participate in the study or confounds the ability to interpret data from the study. For Example:
 - symptomatic congestive heart failure of New York Heart Association Class III or IV (Appendix 13.5)
 - unstable angina pectoris, symptomatic congestive heart failure, myocardial infarction within 6 months of start of study drug, serious uncontrolled cardiac arrhythmia or any other clinically significant cardiac disease
 - severely impaired lung function with O₂ saturation that is 88% or less at rest on room air
 - active (acute or chronic) or uncontrolled severe infections
 - condition requiring ongoing use of medications that are considered STRONG or MODERATE CYP3A4 inhibitors or inducers and P-gp substrates at study screening. However, those who require weak inhibitors/inducers can be enroll at discretion of the PI. See Appendix 13.2 for a list of excluded and cautionary concomitant medications.
 - liver disease such as cirrhosis or severe hepatic impairment (Child-Pugh class C).
- 4. Has a history (within the past 12 months) of (non-infectious) pneumonitis requiring systemic steroids, or active pneumonitis.
- 5. Bilirubin < 3 × ULN in the presence of liver metastases or presence of documented Gilbert's syndrome (unconjugated hyperbilirubinemia)
- 6. Concurrent use of other anti-cancer agents or therapies during study treatment.
- 7. Use of any other experimental drug or therapy within 28 days of initiating treatment with the investigational agents.
- 8. Known seropositive for or active viral infection with human immunodeficiency virus (HIV), hepatitis C (HCV), or hepatitis B virus (HBV); patients who are seropositive because of hepatitis B virus vaccine are eligible.
- 9. Previous use of JAK1 inhibitor (itacitinib), or history of progression on everolimus.

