- All subjects will be treated prophylactically with an antiviral agent (e.g., acyclovir) to prevent varicella re-activation or other viral infections

Inhibitors of CYP3A4 and/or P-gp

Co-administration with strong inhibitors of CYP3A4 (e.g., ketoconazole, itraconazole, ritonavir) or P-glycoprotein (P-gp) should be avoided. See Appendix 13.2 for detailed list of medications.

Itacitinib + everolimus in HL

Version 11.0

Page 42 of 72

Co-administration with moderate CYP3A4 inhibitors (e.g., erythromycin, fluconazole) or P-gp inhibitors should be used with caution. If subject requires co-administration of moderate CYP3A4 inhibitors or P-gp inhibitors, reduce the dose of everolimus to half the currently used dose. If the inhibitor is discontinued the everolimus dose should be returned to the dose used prior to initiation of the moderate CYP3A4/P-gp inhibitor.

Seville orange, star fruit, grapefruit and their juices affect P450 and P-gp activity. Concomitant use should be avoided.

See Table 7 for a summary of actions to be taken when the use of a CYP3A4/P-gp inhibitor is required.

Table 7: Recommended Dosage Modifications for Concurrent Use of a P-gp substrate or CYP3A4 Inhibitor

Type of CYP3A4 inhibitor or P-gp substrate	ACTION TAKEN
Strong Inhibitor	For temporary use – discontinue both agents (everolimus and itacitinib) until completion of inhibitor therapy. For extended use (> 28 days) – discontinue from study.
Moderate Inhibitors	Reduce treatment of both agents (everolimus and itacitinib) to 50% during treatment with moderate inhibitors.
Weak Inhibitors	Use caution. No treatment adjustments required.

Note: See appendix 13.2 for a list of CYP3A4 inhibitors and P-gp substrates

Inducers of CYP3A4 and/or P-gp

Avoid the use of strong CYP3A4 inducers. If subject requires co-administration of strong CYP3A4 inducers (i.e., phenytoin, carbamazepine, rifampin, rifabutin, phenobarbital, St. John's wort), he or she should be removed from study. See Appendix 13.2 for detailed list of medications.

See Table 8 for a summary of actions to be taken when the use of a CYP3A4 inducer or P-gp substrate is required.

Table 8: Recommended Dosage Modifications for Concurrent Use of a P-gp substrate or CYP3A4 Inducer

Type of P-gp substrate or CYP3A4 Inducer	ACTION TAKEN
Strong Inducer	For temporary use - Use caution. No treatment adjustments required. For extended use (> 28 days) – discontinue from study.
Moderate Inducer	Use caution. No treatment adjustments required.

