Weak Inducer	Use caution. No treatment adjustments required.

Note: See appendix 13.2 for a list of P-gp substrate or CYP3A4 Inducer

Itacitinib + everolimus in HL
Version 11.0
Page 43 of 72

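### Appendix 13.2 puts four drugs in two lists with different eligibility or dose consequences, and no rule says which listing governs

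*Combined protocol and SAP*

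**What the plan says.** Appendix 13.2 divides interacting drugs under two headings, Excluded and Cautionary, and within each by mechanism and strength.

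- Excluded, moderate CYP3A inhibitors: the list opens "amprenavir, aprepitant, atazanavir, ciprofloxacin, crizotinib".
- Cautionary, weak CYP3A inducers: "amprenavir, aprepitant, armodafinil, clobazamechinacea, pioglitazone, prednisone, rufinamide, vemurafenib".
- Cautionary, weak CYP3A inhibitors: the list opens "alprazolam, amiodarone, amlodipine, atorvastatin, bicalutamide" and later includes ticagrelor.
- Cautionary, P-gp inhibitors: the list includes amiodarone and ticagrelor.

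Exclusion criterion 3 (Section 4.2) bars conditions needing ongoing use of strong or moderate CYP3A4 inhibitors or inducers at screening. It adds that "those who require weak inhibitors/inducers can be enroll at discretion of the PI" and sends the reader to Appendix 13.2 for the lists.

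For use on study, Section 6.2 gives running text and two tables. The text halves everolimus for a moderate CYP3A4 inhibitor or a P-gp inhibitor. Table 7, for moderate inhibitors, says: "Reduce treatment of both agents (everolimus and itacitinib) to 50% during treatment with moderate inhibitors". For weak inhibitors (Table 7) and weak inducers (Table 8) the entry is the same: "Use caution. No treatment adjustments required".

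**The concern.** Exclusion 3 relies on the appendix to separate drugs that bar entry from drugs that do not. For aprepitant and amprenavir the appendix returns both answers. Once a subject is on study, the same two listings lead to different rows of Tables 7 and 8. For amiodarone and ticagrelor, one listing leads to a table row with no adjustment and the other to a sentence that halves everolimus.

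At stake is consistent handling. Two members of staff could enrol or dose the same subject differently, each following the text. The protocol states that both study drugs are metabolised by CYP3A4 (Sections 1.6 and 6.2), so these rules bear on exposure and safety. They also touch the tolerability review, which requires the cohort-specific dose on at least 75% of the 28 days of Cycle 1, or a DLT (Sections 3.2, 7.3 and 7.7).

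**Working it through.** The plan gives no figure to reproduce here, so the check sets the passages side by side.

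**Step 1. Find the duplicates.** Appendix 13.2 has seven drug lists: strong and moderate inhibitors and strong and moderate inducers under Excluded; weak inhibitors, weak inducers and P-gp inhibitors under Cautionary. Matching on the exact printed name gives four drugs in more than one list: amprenavir, aprepitant, amiodarone and ticagrelor. If ronalzine in the P-gp list is a misspelling of ranolazine in the weak-inhibitor list, there is a fifth. That is an assumption and is not counted.

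**Step 2. Map each listing to its consequence.**

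| Drugs | Listing | At screening (exclusion 3) | On study |
|---|---|---|---|
| Aprepitant, amprenavir | Moderate CYP3A inhibitor (Excluded) | Ongoing use barred | Both agents to 50% (Table 7); everolimus alone halved (6.2 text) |
| Aprepitant, amprenavir | Weak CYP3A inducer (Cautionary) | Investigator's discretion | No adjustment (Table 8) |
| Amiodarone, ticagrelor | Weak CYP3A inhibitor (Cautionary) | Investigator's discretion | No adjustment (Table 7) |
| Amiodarone, ticagrelor | P-gp inhibitor (Cautionary) | Also cautionary, so no conflict arises from the two listings | Everolimus halved (6.2 text) |

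The first pair differs on eligibility and on dose; the second pair differs on dose only.

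**Step 3. Look for something that settles it.** No precedence rule appears in Section 4.2, Section 6.2, the notes to Tables 7 and 8, or the appendix. Two further mismatches stand in the way of inferring one:

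- For moderate inhibitors, the 6.2 text and Table 7 agree on halving everolimus but not on whether itacitinib is also reduced. This affects every drug in the moderate-inhibitor list.
- Section 6.2 introduces Table 7 as covering CYP3A4 and P-gp inhibitors, but the table's title, column heading and note speak of P-gp substrates. Exclusion 3 and Table 8 also say substrates. Appendix 13.2 lists P-gp inhibitors and has no substrate list. The tables therefore do not settle the action for a P-gp inhibitor.

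**Step 4. Possible reach into the DLT data.** 75% of 28 days is 0.75 × 28 = 21 days, which leaves 28 − 21 = 7. A subject without a DLT who is off the cohort-specific dose for more than 7 days of Cycle 1 drops out of the tolerability review. A dose reduction required under one listing and not under the other could therefore change evaluability. In a cohort of 3 to 6, one subject is between 1/6 = 17% and 1/3 = 33% of the cohort. The documents do not say how many subjects, if any, would take these drugs.

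**The case against.** The strongest reply is that the lists sort drugs by mechanism, and a drug can have more than one. Read cumulatively, every applicable rule is followed: a table row that requires no adjustment for a weak inducer does not cancel one that another row requires because the drug is also a moderate inhibitor. Likewise, the sentence in exclusion 3 about weak agents does not say that it lifts the bar on moderate ones. On that view a reader who infers that the protocol gives opposite instructions, or that dual listing is itself a classification error, goes too far. That much stands: the documents do not show that any drug is misclassified, and the two listings can be reconciled. But no passage states the cumulative reading, so staff must supply it.

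Other parts of the reply also stand.

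- Entry with a weak inducer is at the investigator's discretion, not automatic.
- The amiodarone and ticagrelor question concerns dose only.
- A reader might take from Table 7 that the first pair's listings differ by half the dose of both agents. The 6.2 text reduces everolimus alone, so that size is not established.
- Section 6.2 requires consultation before excluded drugs are taken, and the appendix calls its lists non-exhaustive and its strength grading not always categorical. Clinical judgement is therefore expected.
- Subjects made non-evaluable by dose changes may be replaced (Sections 3.1.2, 7.3 and 7.7), which limits the effect on the DLT data.
- If amprenavir is used only for HIV, which is an assumption here, exclusion 8 leaves little practical scope for it. The other three drugs remain.

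**Conclusion.** The point holds as a gap in internal consistency. Four drugs have two listings each, the listings carry different consequences, and nothing says which governs. For aprepitant and amprenavir the difference covers eligibility (barred, or at the investigator's discretion) and on-study dose (a reduction, or none). For amiodarone and ticagrelor it is the dose action alone (no adjustment, or everolimus halved). Under these listings the everolimus dose differs by half; whether itacitinib also differs for the first pair depends on the unresolved disagreement between Table 7 and the 6.2 text.

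The count of four rests on exact spelling in the lists as printed. No sample size, error rate or decision boundary changes, and the number of subjects affected is unknown. The reason to act is consistent and safe handling of subjects, at very small cost.

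**What to change.** Reconcile exclusion criterion 3, Section 6.2, Tables 7 and 8 and Appendix 13.2:

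1. State which eligibility rule and which dose action govern when a drug is in more than one list.
2. Make the 6.2 text and Table 7 agree on which agents are adjusted for a moderate inhibitor.
3. Use one P-gp term, inhibitor or substrate, consistently in exclusion 3, the 6.2 text, both tables and the appendix, and make clear which action applies to the appendix's P-gp list.

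A drug need not be confined to one list; keeping it under two mechanisms is acceptable once the governing rule is stated. The category and the action are for the sponsor and pharmacist to decide, and none is proposed here.

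The cost is a text edit to those five places, which is more than the appendix alone because eligibility and dosing wording is involved. The design, sample size and analysis are unchanged.
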